#### 10. Sponsor and Investigational Site Requirements (Study Administration)

#### 10.1 Ethics

### 10.1.1 Ethical Conduct of the Study

This study will be conducted in accordance with the ethical principles that have their origins in the Declaration of Helsinki.

A description of this clinical trial will be available on http://www.ClinicalTrials.gov, as required by U.S. Law.

#### 10.1.2 Institutional Review Board

The sponsor and investigator(s) shall assure that an IRB, constituted in accordance with 21CFR812 Subpart D and ICH guidelines for GCP (ICH E6 GCP) will provide initial and continuing review of the study.

Prior to enrollment of study subjects in the image acquisition portion of the study, documented IRB approval of the protocol, the informed consent form, and any other written materials supplied to the subjects, including any advertisements for subject recruitment, was obtained and provided to the sponsor or its designated representative(s).

May 15, 2018 Confidential Page 24 of 31 DOC-0038502-A Final 1.0

Prior to commencement of the reader study portion of the study, documented IRB approval of the protocol, the reader informed consent form, and any other written materials supplied to the readers must be obtained by the sponsor or its designated representative(s).

The IRB must also be informed of any protocol amendments prior to implementation. The sponsor must provide reports of any change in research activity (e.g., the completion, termination, or discontinuation of the study) to the IRB. Annual review documentation will be submitted to the IRB 90 days prior to the IRB approval expiration.

#### 10.2 Reader Informed Consent

Each reader must provide written informed consent before participating in the reader study of this protocol.

#### 10.3 Protocol Compliance

Except for a change that is intended to eliminate an apparent immediate hazard to a study subject, the protocol shall be conducted as described. Any such change must be reported immediately to Fujifilm or its representative(s) and the governing IRB.

#### 10.3.1 Protocol Amendments

Protocol amendments will be prepared and approved by Fujifilm or its authorized designee. All protocol amendments will be signed by the investigator and submitted to the IRB for review prior to implementation. Documentation of IRB approval must be provided to Fujifilm or its representative. If an amendment significantly alters the study design, increases potential risk to the subject, or otherwise affects statements in the informed consent, the informed consent must be revised and submitted to the IRB for review and approval. The approved informed consent form must be used to obtain consent from new subjects enrolled in the study and must also be used to re-consent subjects already enrolled in the study, if they are affected by the amendment.

### 10.4 Retention of Study Records

All documents pertaining to the conduct of this clinical study – including CRFs, informed consent forms, source documents, and other records must be retained during the investigation, unless otherwise requested by the sponsor, for a period of 2 years after the later of the following 2 dates [21CFR812.140 (d)]:

 Records are no longer required for the purposes of supporting a regulatory submission to the FDA.

#### OR

• Following the termination or withdrawal of the regulatory submission.

The principal investigator must contact Fujifilm in writing prior to the destruction of any study records or in the event of accidental destruction or loss of the documents. If the principal investigator leaves the institution where the study is being conducted, the principal investigator must contact the sponsor to arrange for transfer of responsibilities and alternative record storage options, if applicable.

Study documentation includes all CRFs, data correction forms, source documents, monitoring logs, sponsor-investigator correspondence, protocols and amendments, ethics committee correspondence and approvals, signed consent forms, etc. Source documents include all original records or observations, results and activities necessary to reconstruct and evaluate the study.

#### 10.5 Data Collection and Management

#### 10.5.1 General

All data entry will be completed using paper Case Report Forms, following the guidelines established in the Data Management Plan.

The privacy of participating subjects must be maintained in accordance with the HIPAA privacy ruling and disclosed per 24CFR50.

The CRFs will be data entered, and then reviewed for accuracy and completeness by a study monitor representing Fujifilm, as well as reviewed by DMC staff prior to data transfer to the statistician.

### 10.5.2 Data Management Center

The responsibilities of the DMC will include monitoring and oversight of the collection efforts, performance of the data audits, facilitating data entry into a computerized database, and providing the data to the statistician.

The DMC responsibilities will include oversight of the data collection efforts (excluding image data, which will be collected by Fujifilm or its designees), facilitation of data entry into the computerized database, all final data cleaning, and performance of a final data quality-control audit prior to database lock.

CRFs will be logged and tracked when received by the DMC. CRFs will then be entered and stored in a 21 CFR Part 11 compliant clinical database. Upon completion of the study and resolution of all outstanding DCFs, the database will be locked and datasets necessary for analysis and reporting will be generated and provided to the statistician for final analysis.

#### 10.6 Confidentiality

#### 10.6.1 Subject Confidentiality

To maintain subject confidentiality, no identifying patient data will be displayed. Unique image identifiers associated with the case ID number will be visible on each image for tracking purposes. A unique ID, one per case per modality will be assigned to each case whose images are selected for the reader study and will be the only subject identifier on all study-related documentation.

Prior to the initiation of the study, Fujifilm or its authorized representative will provide the readers with adequate training related to the identification. The subject's unique identifier may be displayed on the softcopy image as an overlay. The overlay may be turned on and off as necessary during the reader studies for reference.

#### 10.6.2 Reader Confidentiality

Information collected during the reader study will be reported in such a way as to preclude identification of any individual radiologist's performance. To maintain reader confidentiality, a unique ID number will be assigned to each radiologist participating in the reader study for entry on the CRF's. A master list of these ID numbers for the radiologists participating in the reader study will be securely maintained by the Fujifilm project manager.

### 10.6.3 Transfer of Confidential Information to the Sponsor or the DMC

This reader study utilizes data from the Fujifilm library that was obtained in Fujifilm protocol FMSU2013-004A. All data utilized for this study (photocopies of radiology, pathology and clinical reports as well as images) was de-identified prior to removal from the acquisition center(s).

### 10.7 Study Monitoring

Fujifilm and/or its designees will monitor the study, verify the collection of data, and confirm that the study is being conducted according to the protocol. The CRF data will be recorded.

The study may be audited by representatives from the FDA or other regulatory agencies, who also shall be allowed access to study documents.

If Fujifilm, the principal investigator, the IRB, or a regulatory authority discover conditions arising during the study that indicate that the study should be halted or that the study center's participation in the study should be terminated, this action may be taken after appropriate consultation between Fujifilm, its designee, and the investigator(s).

### 10.8 Sponsor Audits

Individuals appointed by the sponsor may visit the CRO to conduct an audit of the study GCPs. The purpose of the visit will be to determine adherence to the protocol, applicable regulations and the sponsor's procedures in addition to the assessing the accuracy of the study data (Inspection Readiness). Prior to initiating this audit, the CRO will be contacted by the sponsor to arrange a convenient time for this visit.

#### 10.9 Inspection by a Regulatory Agency

At some point during the study, the investigator may be visited by a regulatory agency (e.g., FDA) to conduct an inspection of the study. The purpose of this visit will be to determine adherence to the protocol and regulatory requirements for conducting clinical studies. The investigator must immediately notify Fujifilm when contacted by a regulatory agency for the purposes of conducting an inspection of the Fujifilm's study.

#### 10.10 Financial Disclosure

In accordance with 21CFR54, the principal investigator and the study readers will provide Fujifilm or its designee sufficient and accurate information on financial interests (proprietary or equity interests and payments exclusive of clinical study costs) to allow complete disclosure documenting lack of conflict of interest. The principal investigator and study readers shall promptly update this information with any relevant changes that occur during the course of the study, at the completion of the study, and for a period of 1 year following the completion of the study.

### 10.11 Study or Study-site Termination

If Fujifilm, the principal investigator, the IRB, or a regulatory authority discover conditions arising during the conduct of the study that indicate that the study should be halted or that the study center should be closed, this action may be taken after appropriate consultation between Fujifilm and the principal investigator. Conditions that may warrant termination of the study include, but are not limited to, the following:

 A decision on the part of Fujifilm to suspend or discontinue testing, evaluation, or development of a product.

The study center may warrant closure/termination for the following reasons:

- Failure of the investigator to comply with pertinent regulatory authority regulations.
- Knowing submission of false information from the research center to Fujifilm, study monitor, or a regulatory authority.
- Insufficient adherence to the protocol requirements.

Study termination and follow-up will be performed in compliance with the conditions set forth in 21CFR812.150 (a) (2).

### 11 Appendices

### Appendix A: Fujifilm FFDM and DBT Image Acquisition and Display

Note: The proposed brand and/or configuration of the ASPIRE products are subject to change.

### Overview of ASPIRE Cristalle DBT Option and ASPIRE Bellus II

Fujifilm's **ASPIRE Cristalle** DBT Option (**Figure A**) mammography acquisition system generates both FFDM and DBT images. It is comprised of the X-ray exposure unit and acquisition workstation, and is FDA PMA approved (P160031) for 2D mammography and DBT image acquisition.

Fujifilm's **ASPIRE Bellus II** (**Figure B**) mammography review workstation displays and supports the physician's review of 2D mammography and DBT images. It is composed of the display accessories of the ASPIRE Cristalle and includes the major components of a PC (with image review and manipulation software installed), a console monitor, and two high-resolution grayscale diagnostic display monitors, and is FDA cleared (K171463)

[figure not shown]

Figure B. ASPIRE Bellus II - Fujifilm's mammography viewer.

### Acquisition of FFDM and DBT Images by ASPIRE Cristalle DBT Option (Figure A)

All FFDM and DBT images of the enrolled study subjects were acquired on the ASPIRE Cristalle system with DBT option. For each study subject, the DBT and FFDM images were acquired under the same breast compression for each of the LCC, RCC, LMLO and RMLO views.

#### Display of FFDM and DBT Images on ASPIRE Bellus II (Figure B)

Mammography images are displayed on the ASPIRE Bellus II for the physician's review. The console allows the user to manage various aspects of the system configurations and setup, including the modality work list, local archive, communications, and the selection of images to be displayed on the two high-resolution grayscale diagnostic display monitors. The viewer supports typical image-manipulation functions, such as windowing, leveling, zooming, etc.

### Appendix B: Inclusion and Exclusion Criteria from FMSU2013-004A

### **Study Population**

All female subjects, of any ethnic or racial origin, who are appearing for a routine screening examination or have been referred for further diagnostic evaluation after a screening examination (within 60 days) or have a 4-view mammogram (within 60 days) due to clinical concerns and receive a BI-RADS assessment of category 4 or 5 after diagnostic workup and are scheduled for biopsy will be eligible to participate in the study.

Subjects will receive a written explanation of the study and will be asked to provide written informed consent to participate. Once eligibility is confirmed and informed consent has been obtained, the subjects will be enrolled in the study.

#### Inclusion Criteria

Subjects enrolled must meet all the following inclusion criteria:

- Screening Subjects
  - o Be at least 40 years of age, are
  - Asymptomatic,
  - Scheduled for a routine screening mammogram,
- Recall Subjects
  - Be at least 18 years of age
  - Received a BIRADS 0 within the last 60 days
  - Are recalled for additional imaging
- Diagnostic Subjects
  - Be at least 18 years of age,
  - Scheduled for a biopsy due to an assessment of BI-RADS® 4 or 5 after diagnostic work-up of a suspicious screening or clinical finding within the last 60 days.
- Have the ability to understand the requirements of the study, to provide written informed consent, and to comply with the study protocol, and
- Meet none of the exclusion criteria.

#### **Exclusion Criteria**

Subjects will be excluded from participating in the study if they meet any one or more of the following exclusion criteria:

- Presence of a breast implant.
- Women with only a single breast; for example, post mastectomy patients.
- Is pregnant or believes she may be pregnant.
- A woman who has delivered and who has expressed the intention to breast-feed or is currently breast-feeding.
- A woman who has significant existing breast trauma within the last one year.
- Has self-reported severe non-focal or bilateral breast pain affecting subject's ability to tolerate digital mammography and/or breast tomosynthesis examinations.
- A woman who has had a mammogram performed for the purpose of therapy portal planning within the last year.
- Cannot, for any known reason, undergo follow-up digital mammography and/or breast tomosynthesis examinations (where clinically indicated) at the participating institution.
- Is an inmate (see US Code of Federal Regulations 45CFR46.306)

May 15, 2018 Confidential Page 31 of 31 DOC-0038502-A Final 1.0

Statistical Analysis Plan

July 16, 2018

FMSU2017-003: A Feature Comparison Study to Evaluate the Modified Processing of Fujifilm's ASPIRE Cristalle with Digital Breast Tomosynthesis Option as Compared to the Original Processing

FUJIFILM Medical Systems U.S.A., Inc.

NCT03586583

Statistical Considerations for FUJIFILM Medical Systems, U.S.A., Inc. protocol FMSU2017-003

1. Statistical Analysis Plan:

The primary objective of the study is to test the non-inferiority of the modified processing in each of 7 general mammographic features. The proportion of cases where the readers judged the modified image processing as non-inferior will be calculated. Non-inferiority is defined as a score of equivalence between modified and original processing or a score indicating the modified image processing is superior. For each reader, the proportion of cases judged as non-inferior with modified processing will be calculated for each feature and each view. A pooled estimate will also be calculated where the results over all readers and views will be combined. 95% percentile bootstrap CIs will be constructed for the pooled proportions of cases judged as non-inferior with the modified processing. These CIs will be reported for each feature.

The null hypothesis is that the pooled proportion of cases judged as non-inferior with modified image processing is ≤ 0.50 , versus the alternative hypothesis that the pooled proportion is >0.50. If the 95% CI did not contain values ≤ 0.50 , then the null hypothesis will be rejected. These hypotheses will be evaluated for each of the seven general mammographic features. If the null hypothesis is rejected for each of the seven general features, then it will be concluded that the readers' subjective evaluation of the features on the modified imaging is non-inferior to the original imaging.

2. Sample Size Justification:

The following assumptions were made for determining sample size for the primary objectives:

- One breast per subject (two views)
- Each of six readers scores an independent sample of cases; thus, there is no correlation between readers' interpretations.
- 50% of cases have dense breasts
- >80% power is required
- 2.5% type I error rate (Note that hypothesis rejection depends on the lower bound of the 95% CI being greater than 0.50.)

Based on these assumptions, sample size was determined as follows:

$$M = \frac{\{1.96 \times \sqrt{0.5(1-0.5)} + 0.84\sqrt{p(1-p)}\}^2}{[p-0.5]^2}$$

where p is the proportion of comparisons judged as non-inferior under the alternative hypothesis. The sample size is given by N=M/(# readers). Table 1 summarizes the number of subjects needed per reader as a function of the proportion of cases judged as non-inferior with the modified processing.

#	Proportion of Comparisons Judged as Non-inferior with				
readers	Modified Processing (DVIIm plus ISR)				
	0.55	0.56	0.57	0.60	
6	131	91	67	33	

Table 1. Number of Sub	bjects Needed Per Reade	er for Tests of Non-inferiority
------------------------	-------------------------	---------------------------------

A study with 600 total subjects (i.e. 100 cases evaluated per reader) was proposed. This sample size would provide slightly more than 80% power to reject the primary null hypothesis, as long as \geq 56% of cases are judged non-inferior.

3. Randomization

Cases will be randomly selected from Fujifilm's existing library (collected under protocol FMSU2013-004A). A stratified randomization will be used where the strata and proposed sampling proportions are summarized in Table 2. Within each stratum, cases will be randomly selected so that approximately 10% would have extremely dense breasts, 40% would have heterogeneously dense breasts, 40% would have scattered fibroglandular breasts, and 10% would have fatty breasts.

Stratum, defined by Reference Standard*	# available subjects	Overall sample composition	# cases per reader	Total # cases
Cancer: (N=229) Architectural Distortion Microcalcification Asymmetry Mass Other	21 86 19 95 8	38%	3-4 14-15 3-4 15-16 1-2	21 86 19 95 8
Biopsy Benign: (N=457) Architectural Distortion Microcalcification Asymmetry Mass Other	19 212 43 158 25	32%	3-4 10 7-8 9 2-3	19 60 43 54 15

Table	2.	Sam	nling	Plan
IUDIC	_	Juin	PIIIS	I Iull

Recalled/No Biopsy	98	10%	10	60
Negative	234	10%	10	60
Unknown	209	10%	10	60
Total	1227	100%	100	600

Because there are subjects with multiple lesions, cases in the table were organized first by the presence/absence of a malignant lesion, and then by presence/absence of an AD (and possibly another lesion), microcalcification, asymmetry, mass, and other, respectively.

For each reader, a randomization list with 100 unique cases will be created consisting of four blocks:

- Block 1: 50 breasts from 50 subjects where the reader scored the CC view,
- Block 2: 50 breasts from a second sample of 50 subjects where the reader scored the MLO view,
- Block 3: same 50 breasts as in Block 1, but re-ordered and scored with the MLO view, and
- Block 4: same 50 breasts as in Block 2, but re-ordered and scored with the CC view.

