### **Definitions**

	Ţ
ACR® BI-RADS®	a. The breasts are almost entirely fatty
Breast Tissue	b. There are scattered areas of fibroglandular density
Composition	c. The breasts are heterogeneously dense, which may obscure small masses
(Density) Categories	d. The breasts are extremely dense, which lowers the sensitivity of mammography
	Assigned by reader; 0 = Incomplete - Need Additional Imaging Evaluation and/or Prior Mammograms for Comparison
	1 = Negative
	2 = Benign
ACR ® BI-RADS ® Assessment Categories	3 = Probably Benign. Management: Short-interval (6-month) follow-up or continued surveillance mammography
Categories	4 = Suspicious. Management: Tissue diagnosis.
	4A = Low suspicion for malignancy
	4B = Moderate suspicion for malignancy
	4C = High suspicion for malignancy
	5 = Highly Suggestive of Malignancy
ASPIRE Bellus II	Fujifilm mammography viewer (see Appendix A) where the FFDM and DBT images are displayed and reviewed by the physician.
ASPIRE Cristalle with DBT Option	Fujifilm's Mammography Acquisition System (see Appendix A) which generates both FFDM and DBT images.
Benign Case	A case in which all lesions are confirmed as benign by a biopsy or surgery and no other lesions are biopsy-malignant.
Cancer Case	A case in which at least one lesion is confirmed as malignant by biopsy or surgery.
Case	Two views (CC and MLO) of one breast.
	Each DBT Examination has two parts:
DBT Examination	
 
Acquisition: Acquisition of DBT images for each of the standard bilateral CC and MLO views (RCC, LCC, RMLO, LMLO) using the ASPIRE Cristalle.
 
Review: DBT images are displayed and interpreted by the physician on the ASPIRE
 

	Bellus II.
DBT Images	A series of mammograms, which are reconstructed from multiple low-dose projection images captured by the ASPIRE Cristalle with the x-ray tube rotated at a number of small offset angles over a limited angular range while the breast remains compressed and unmoved.
DBT Read	The physician reads (interprets) the DBT images displayed on the ASPIRE Bellus II (see Appendix A)
DBT Views	A series of cross-sectional views of the DBT images for each of the CC and MLO views for each breast.

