#### **General instructions** for the readers are as follows:

The reader is to compare the tomosynthesis image on the left monitor to the tomosynthesis image on the right monitor. One CRF will be completed for each view (CC and MLO) for each case (breast).

For each case that has a lesion, the reader is to document lesion type, quadrant and slice number.

A study scribe representing the sponsor will capture the radiologist's results on the CRFs to ensure completeness and allow the radiologist to focus on evaluation of image sets.

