### 9. Statistical Analysis

The proportion of cases where the readers judged the modified image processing as non-inferior will be calculated. Non-inferiority will be defined as a score of equivalence between modified and original or a score indicating the modified image processing is superior. For each reader, the proportion of cases judged as non-inferior with modified processing will be calculated for each feature and each view in Table 3. A pooled estimate will also be calculated where the results over all readers and views will be combined. 95% percentile bootstrap CIs will be constructed for the pooled proportions of cases judged as non-inferior with the modified processing. These CIs will be reported for each feature.

The null hypothesis is that the pooled proportion of cases judged as non-inferior with modified image processing is  $\leq$ 0.50, versus the alternative hypothesis that the pooled proportion is >0.50. If the 95% CI does not contain values  $\leq$ 0.50, then the null hypothesis will be rejected. These hypotheses will be evaluated for each of the seven general mammographic features. If the null hypothesis is rejected for each of the seven general features, then it will be concluded that the readers' subjective evaluation of the features on the modified imaging is non-inferior to the original imaging.

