### 9.2 Analysis of Primary Objective

The primary objective of this study is non-inferiority in each of the seven general mammographic features of the modified processing.

The proportion of cases where the readers judged the modified image processing as non-inferior will be calculated. Non-inferiority will be defined as a score of equivalence between modified and original or a score indicating the modified image processing is superior. For each reader, the proportion of cases judged as non-inferior with modified processing will be calculated for each general mammographic feature. A pooled estimate will also be calculated where the results over all readers will be combined. 95% percentile bootstrap CIs will be constructed for the pooled proportions of cases judged as non-inferior with the modified processing. These CIs will be reported for each of the 7 general mammographic features.

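### Does the unstated bootstrap unit, with Protocol 9.2 leaving out views, put the 2.5% error at risk?

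*SAP*

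**What the plan says.** SAP 1, Protocol 9 and the synopsis (Study Analysis) describe one rule. A proportion is taken per reader, feature and view, and then: "A pooled estimate will also be calculated where the results over all readers and views will be combined". The result is compared with 0.50 through an interval that is described only in these words: "95% percentile bootstrap CIs will be constructed for the pooled proportions of cases judged as non-inferior with the modified processing". All seven features must pass. SAP 2 states a 2.5% error and ties it to that interval: "hypothesis rejection depends on the lower bound of the 95% CI being greater than 0.50".

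Protocol 9.2 repeats this more briefly and leaves out views. It says "For each reader, the proportion of cases judged as non-inferior with modified processing will be calculated for each general mammographic feature", and then "A pooled estimate will also be calculated where the results over all readers will be combined".

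The protocol's Definitions describe a case as "Two views (CC and MLO) of one breast". Section 8.4.4 asks for a separate form for each view, and SAP 3 has the same reader score the two views of a breast in different blocks. Each case therefore carries two scores per feature.

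The sample-size text in both documents introduces its parameter with "where p is the proportion of comparisons judged as non-inferior under the alternative hypothesis", while its closing sentence speaks of cases. Nowhere is it said what the bootstrap resamples.

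**The concern.** The lower limit of this interval is the whole decision rule, so its construction matters. The same reader scores both views of the same breast, and those two scores are likely to be correlated. The stated independence assumption covers readers only and is silent on views. An analyst who stacks 1,200 rows per feature and resamples rows would get an interval that is too narrow, and the real error would exceed the stated 2.5%.

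The wording of 9.2 adds a second worry. If it meant one yes/no verdict per case, the answer would depend on how two views are combined. Take 56% non-inferior per view and an assumed correlation r = 0.5. Then p² + r·p(1−p) = 0.3136 + 0.1232 = 43.7% of cases would pass on both views. On at least one view, 1 − (0.1936 + 0.1232) = 68.3% would pass. These lie on opposite sides of 0.50, so at first sight the quantity being tested looks undefined.

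**Working it through.** **Inputs from the documents.** Six readers with 100 cases each, so 600 cases and 1,200 view scores per feature; null value 0.50; one-sided error 2.5%; power at least 80%; planned alternative p = 0.56 (SAP 1 and 2; Protocol 9 and 9.3).

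**Assumed.** The correlation r between the CC and MLO results of a case is not given, so r = 0.3 / 0.5 / 0.7 is used, with the extremes 0 and 1 where they help. The six readers are treated as fixed.

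**1. The plan's own table.** M = {1.96·√0.25 + 0.84·√(p(1−p))}² / (p − 0.5)². At p = 0.56 this is (0.98 + 0.84 × 0.4964)² / 0.0036 = 542.1, and 542.1/6 = 90.3, rounded up to 91. For p = 0.55 / 0.57 / 0.60, M/6 = 130.3 / 66.3 / 32.3, giving 131 / 67 / 33. All four entries match.

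**2. Power at 600, one result per case.** Φ[(0.06·√600 − 0.98)/0.4964] = 83.8%, in line with the claim of slightly more than 80%. The calculation takes no credit for the second view. Had the plan counted the two views as independent, the requirement at 0.56 would have been 542.1/12 = 45.2, or 46 subjects per reader, and not 91.

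**3. Whole cases resampled within reader, both views kept together.** The pooled estimate is the mean of the two view indicators, with variance p(1−p)(1+r)/1,200. Resampling cases reproduces this variance, so the error stays at its nominal value. In simulation (six fixed readers, 100 cases each, reader offsets with SD 0 or 5 percentage points, 20,000 runs of 1,000 draws) the one-sided error was 2.44 to 2.60%. Power at 0.56 is Φ[(0.06·√(1,200/(1+r)) − 0.98)/0.4964]:

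| r | effective n = 1,200/(1+r) | power |
|---|---|---|
| 0.3 | 923 | 95.5% |
| 0.5 | 800 | 92.6% |
| 0.7 | 706 | 89.2% |
| 1 | 600 | 83.8% |

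The worst case is the figure from step 2.

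**4. View scores resampled singly.** The bootstrap variance is then p(1−p)/1,200, while the true variance is (1+r) times larger. The one-sided error is 1 − Φ(1.96/√(1+r)):

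| r | error per feature | simulated |
|---|---|---|
| 0 | 2.5% | – |
| 0.3 | 4.3% | 4.05–4.36% |
| 0.5 | 5.5% | 5.52–5.58% |
| 0.7 | 6.6% | 6.66% |
| 1 | 8.3% | – |

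**5. Protocol 9.2 beside Protocol 9 and SAP 1.** If the case result in 9.2 is the average of its two view indicators, the pooled estimate is (1/600)·Σ(CC + MLO)/2 = (1/1,200)·Σ(all view scores). With both views scored for every case, this equals the estimate pooled over readers and views. Section 9.2 contains no null hypothesis, no 0.50 threshold and no rule for combining views into a verdict. Those passages that do state the threshold (synopsis, Protocol 9, SAP 1) all name views. Within a single view a case has one score per feature, so a proportion of cases per feature and view is well defined.

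**The case for a change.** The best argument for a change is that a statistician could resample either unit and still comply with the text, while only whole-case resampling delivers the stated 2.5% whatever the correlation. The phrase about pooling over readers and views, and the word comparisons in the sample-size text, could even steer a programmer towards 1,200 separate rows. One sentence in the SAP would settle it at no cost in cases or power.

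What stands is that the resampling unit is not written down, that 9.2 is worded differently from its parent section, and that comparisons and cases are used for the same thing.

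What does not stand is the step from there to a threatened result. The inflated error needs an analyst to ignore an evident pairing in a plan that sizes itself on one breast per subject and, by step 2, gives the second view no weight as extra independent information. The alarming case-verdict percentages rest on a both-views or an either-view rule, and no passage mentions one. The SAP, dated after the protocol, has the full wording with views.

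One caution applies to the reassurance. The power figures here, like the plan's, are per feature, and the chance of passing all seven is lower. That holds whichever unit is resampled and is not evidence for this concern.

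**Conclusion.** No change to the plan is needed. The missing resampling unit is a detail that a competent analyst would fill correctly from the design: 600 cases, two paired scores each, cases drawn within reader. On that reading the error is about 2.5% per feature at any between-view correlation, and per-feature power at 56% is at least 83.8%. The wording of 9.2, and the mix of comparisons and cases, are clerical and do not alter the estimate when both views of every case are scored.

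The exposure, if the pairing were ignored, is a one-sided error of about 4.3 to 6.6% per feature for r between 0.3 and 0.7, with no rise at r = 0. Because all seven features must pass, the per-feature error is an upper bound on the error of the overall conclusion. These results take the six readers as fixed, which fits the conclusion in Protocol 9 and SAP 1 about the readers' own subjective evaluation. The values of r are assumptions, since the documents give none.
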